3.1.1. All Randomized Analysis Set

All Randomized Analysis Set includes all subjects who are randomized in the study. This is the primary analysis set for by-subject listings.

3.1.2. Full Analysis Set

The Full Analysis Set (FAS) includes all randomized subjects who received at least 1 dose of study drug. The study drugs in this study are filgotinib 200 mg, filgotinib 100 mg, adalimumab and PTMs. This is the primary analysis set for efficacy analyses.

3.1.3. Per-Protocol Analysis Set

The Per-Protocol (PP) Analysis Set includes subjects in the FAS who did not have major protocol deviations occurring prior to or on Week 12 that will affect the efficacy analysis, and were compliant (with on-treatment adherence $\geq 80\%$ in the first 12-week period) to study treatment.

Major protocol deviations include the following:

- Violation of at least one of the following key eligibility criteria:
 - 1) Have a diagnosis of RA (2010 ACR/EULAR criteria for RA), and are ACR functional class I-III
 - 2) Have ≥ 6 swollen joints (from swollen joint count based on 66 joints [SJC66]) and ≥ 6 tender joints (from tender joint count based on 68 joints [TJC68]) at both Screening and Day 1 (need not be the same joints)
 - 3) Must meet at least one of the following parameters at Screening:
 - a) ≥ 1 documented joint erosion on radiographs of the hands, wrists or feet by central reading AND a positive result for anti-CCP or RF (based on central laboratory)OR
 - b) ≥ 3 documented erosions on radiographs of the hands, wrists or feet by central reading if both antibodies (ie, RF, anti-CCP) are negative (based on central laboratory)OR
 - c) Serum CRP ≥ 6 mg/L (based on central laboratory)
 - 4) Ongoing treatment with a stable dose of MTX as described in protocol
 - 5) Subjects that have failed prior therapy with a bDMARD are not eligible to participate. Subjects with prior exposure to one bDMARD may be enrolled if there is documented evidence of limited exposure (ie, less than 3 months) to the bDMARD
- Received prohibited concomitant medications
- Background medications were changed in violation of protocol
- Improper study medication administration and unintended medication overdose
- Data were questionable because of significant site quality or compliance issues

Qualifications and identification of the specific major protocol deviations that result in exclusion from the PP Analysis Set will be determined while the study remains blinded, prior to database finalization.

The PP Analysis Set is the secondary analysis set for efficacy analyses on primary and key secondary endpoints at Week 12. Statistical analyses using PP Analysis Set are specified in Section 6.

3.1.4. Safety Analysis Set

The Safety Analysis Set includes all subjects who received at least 1 dose of study drug. This is the primary analysis set for safety analyses.

3.1.5. Pharmacokinetic Analysis Set

The Pharmacokinetic (PK) analysis set includes all subjects in the Safety Analysis Set who have at least 1 nonmissing plasma concentration data for filgotinib and/or its metabolite GS-829845. This is the primary analysis set for general PK analyses.

3.1.6. Pharmacokinetic Substudy Analysis Set

CCI
[REDACTED]

3.2. Subject Grouping

For analyses based on the All Randomized Analysis Set and FAS, subjects will be grouped according to the treatment to which they were randomized. For analyses based on the Safety Analysis Set and PP Analysis Set, subjects will be grouped according to actual treatment received. The actual treatment received will differ from the randomized treatment only when their actual treatment differs from randomized treatment for the entire treatment duration of each treatment period.

The treatment groups during the placebo controlled period are:

- Filgotinib 200 mg q.d.
- Filgotinib 100 mg q.d.
- Adalimumab
- Placebo

The treatment groups during the re-randomized period are:

- Filgotinib 200 mg q.d.
- Filgotinib 100 mg q.d.
- Adalimumab
- Placebo switch to filgotinib 200 mg q.d.
- Placebo switch to filgotinib 100 mg q.d.

For the PK Analysis Set, subjects will be grouped according to the actual treatment they received.

3.3. Strata and Covariates

Subjects will be randomly assigned to treatment groups via the interactive web response system (IWRS) in a 3:3:2:3 ratio to filgotinib 200 mg, filgotinib 100 mg, adalimumab or PTM using a stratified randomization schedule. Stratification will be based on the following variables:

- Geographic region (**Group A** includes the following countries: Australia, Belgium, Canada, France, Germany, Ireland, Israel, Italy, Netherlands, New Zealand, Republic of Korea, South Africa, Singapore, Spain, Sweden, Switzerland, United Kingdom, and USA; **Group B** includes the following countries: Bulgaria, Croatia, Czech Republic, Estonia, Georgia, India, Moldova, Romania, Russia, Slovakia, Ukraine, Serbia, Hungary, Latvia and Poland; **Group C** includes the following countries: Argentina, Brazil, Chile, Colombia, Peru, Puerto Rico and Mexico; **Group D** includes the following countries: China, Hong Kong, Malaysia, Philippines, Taiwan, Thailand and Vietnam; **Group E** includes Japan;
- Prior exposure to bDMARDs (Yes or No)
- Presence of RF or anti-CCP Ab (Yes or No) (Presence of RF = No if RF < 15 IU/mL; Presence of anti-CCP Ab = No if anti-CCP Quant < 17 U/mL)

If there are discrepancies in stratification factor values between the IWRS and the clinical database, the values recorded in the clinical database will be used for analyses.

For efficacy endpoints, stratification factors and the baseline value of the efficacy variable(s) will be included as covariates in the efficacy analysis model, as specified in Section 6.

3.4. Examination of Subject Subgroups

The primary and key secondary efficacy endpoints will be examined using the following subgroups (but not limited to the ones listed below):

- Age (on the first dosing date of any study drug, < 65 or ≥ 65)
- Sex at birth (male or female)
- Race
- Baseline weight (< 60 kg, ≥ 60 kg to < 100 kg or ≥ 100 kg)
- Geographic region (A, B, C, D or E)
- Prior exposure to bDMARDs (Yes or No)
- Presence of RF or anti-CCP Ab (Yes or No)

- Duration of RA diagnosis on the first dosing date of study drug (< 1 year, ≥ 1 year to < 5 years, ≥ 5 years to < 10 years or ≥ 10 years)
- Disease activity on the first dosing date of study drug (DAS28[CRP] ≤ 5.1 or DAS28[CRP] > 5.1)
- Concurrent use of oral corticosteroids on the first dosing date of study drug (Yes or No)
- High-Sensitivity C-reactive Protein (hsCRP) (≥ 4 mg/L or < 4 mg/L)

Lists of bDMARDs and oral corticosteroids are provided in [Appendix 1](#).

3.5. Multiple Comparisons

The primary endpoint for the study is the proportion of subjects who achieve an ACR20 response at Week 12. The primary analyses will consist of a superiority test of filgotinib 200 mg compared to placebo based on the ACR20 response rate at Week 12.

The following hypothesis testing for secondary analyses will commence after the primary analysis reaches statistical significance, and will be tested according to the hierarchical testing principle at the 2-sided 0.05 level. If a null hypothesis is not rejected, formal sequential testing will be stopped and only nominal significance will be reported for the remaining hypotheses:

- 1) Superiority of filgotinib 100 mg compared to placebo based on ACR20 response rate at Week 12
- 2) Superiority of filgotinib 200 mg compared to placebo based on the change from Baseline in HAQ-DI at Week 12
- 3) Superiority of filgotinib 100 mg compared to placebo based on the change from Baseline in HAQ-DI at Week 12
- 4) Superiority of filgotinib 200 mg compared to placebo based on the proportion of subjects with DAS28(CRP) < 2.6 at Week 12
- 5) Superiority of filgotinib 100 mg compared to placebo based on the proportion of subjects with DAS28(CRP) < 2.6 at Week 12
- 6) Superiority of filgotinib 200 mg compared to placebo based on the change from Baseline in mTSS at Week 24
- 7) Superiority of filgotinib 100 mg compared to placebo based on the change from Baseline in mTSS at Week 24
- 8) Non-inferiority of filgotinib 200 mg compared to adalimumab based on the proportion of subjects with DAS28(CRP) ≤ 3.2 at Week 12

- 9) Non-inferiority of filgotinib 100 mg compared to adalimumab based on the proportion of subjects with $\text{DAS28(CRP)} \leq 3.2$ at Week 12
- 10) Superiority of filgotinib 200 mg compared to placebo based on the change from Baseline in SF-36 PCS at Week 12
- 11) Superiority of filgotinib 100 mg compared to placebo based on the change from Baseline in SF-36 PCS at Week 12
- 12) Superiority of filgotinib 200 mg compared to placebo based on the change from Baseline in FACIT-Fatigue at Week 12
- 13) Superiority of filgotinib 100 mg compared to placebo based on the change from Baseline in FACIT-Fatigue at Week 12
- 14) Superiority of filgotinib 200 mg compared to adalimumab based on the proportion of subjects with $\text{DAS28(CRP)} \leq 3.2$ at Week 12
- 15) Superiority of filgotinib 100 mg compared to adalimumab based on the proportion of subjects with $\text{DAS28(CRP)} \leq 3.2$ at Week 12
- 16) Non-inferiority of filgotinib 200 mg compared to adalimumab based on the proportion of subjects with $\text{DAS28(CRP)} < 2.6$ at Week 12
- 17) Non-inferiority of filgotinib 100 mg compared to adalimumab based on the proportion of subjects with $\text{DAS28(CRP)} < 2.6$ at Week 12
- 18) Superiority of filgotinib 200 mg compared to adalimumab based on the proportion of subjects with $\text{DAS28(CRP)} < 2.6$ at Week 12
- 19) Superiority of filgotinib 100 mg compared to adalimumab based on the proportion of subjects with $\text{DAS28(CRP)} < 2.6$ at Week 12

3.6. Missing Data and Outliers

3.6.1. Missing Data

In general, missing data will not be imputed unless methods for handling missing data are specified. Exceptions are presented in this document.

For missing last dosing date of study drug, imputation rules are described in Section 4.2.1. For partial date of initial RA diagnosis, imputation rules are described in Section 5.2. The handling of missing or incomplete dates for AE onset is described in Section 7.1.5.2, and for prior and concomitant medications in Section 7.4. Imputation rules adopted in the efficacy analyses are specified in Section 6.

3.6.2. Outliers

Outliers will be identified during the data management and data analysis process, but no sensitivity analyses will be conducted. All data will be included in the data analyses.

3.7. Data Handling Conventions and Transformations

In general, age (in years) on the date of the first dose of study drug will be used for analyses and presentation in listings. If an enrolled subject was not dosed with any study drug, the randomization date will be used instead of the first dosing date of study drug. For screen failures, the date the last informed consent was signed will be used for age calculation. If only birth year is collected on the CRF, “01 July” will be used for the unknown birth day and month for the purpose of age calculation. If only birth year and month are collected, “01” will be used for the unknown birth day.

Non-PK Data that are continuous in nature but are less than the lower limit of quantitation (LOQ) or above the upper LOQ will be imputed as follows:

- A value that is 1 unit less than the LOQ will be used to calculate descriptive statistics if the datum is reported in the form of “< x” (where x is considered the LOQ). For example, if the values are reported as < 50 and < 5.0, values of 49 and 4.9, respectively, will be used to calculate summary statistics. An exception to this rule is any value reported as < 1 or < 0.1, etc. For values reported as < 1 or < 0.1, a value of 0.9 or 0.09, respectively, will be used for calculate summary statistics.
- A value that is 1 unit above the LOQ will be used to calculate descriptive statistics if the datum is reported in the form of “> x” (where x is considered the LOQ). Values with decimal points will follow the same logic as above.
- The LOQ will be used to calculate descriptive statistics if the datum is reported in the form of “≤ x” or “≥ x” (where x is considered the LOQ).

Natural logarithm transformation will be used for plasma/blood concentrations and analysis of PK parameters. Plasma concentration values that are below the limit of quantitation (BLQ) will be presented as “BLQ” in the concentration data listing. Values that are BLQ will be treated as 0 at predose time points, and one-half the value of the LOQ at postbaseline time points.

The following conventions will be used for the presentation of summary and order statistics:

- If at least 1 subject has a concentration value of BLQ for the time point, the minimum value will be displayed as “BLQ.”
- If more than 25% of the subjects have a concentration data value of BLQ for a given time point, the minimum and Q1 values will be displayed as “BLQ.”
- If more than 50% of the subjects have a concentration data value of BLQ for a given time point, the minimum, Q1, and median values will be displayed as “BLQ.”

- If more than 75% of the subjects have a concentration data value of BLQ for a given time point, the minimum, Q1, median, and Q3 values will be displayed as “BLQ.”
- If all subjects have concentration data values of BLQ for a given time point, all order statistics (minimum, Q1, median, Q3, and maximum) will be displayed as “BLQ.”

PK parameters that are BLQ will be imputed as one-half LOQ before log transformation or statistical model fitting.

3.8. Analysis Visit Windows

3.8.1. Definition of Study Day

The first dose date of individual study drug will be calculated separately for each study drug (ie, filgotinib 200mg, filgotinib 100mg, adalimumab and PTMs) in a treatment group. Study Day 1 is defined as the first dose date of any study drug, which is the minimum of the first dose dates of individual study drugs in a treatment group.

The last dose date of individual study drug will be calculated separately for each study drug in a treatment group. The last dose date for an individual study drug will be the end date on study drug administration CRF for the record where the “study drug was permanently withdrawn” flag is “Yes”. The last dose date of any study drug will be defined as the maximum of the last dose dates of individual study drugs in a treatment group.

Study Day will be calculated from the Study Day 1 and derived as follows:

- For postdose study days: Assessment Date – Study Day 1 + 1
- For days prior to the first dose: Assessment Date – Study Day 1

For subjects who were on placebo and then re-randomized, the On-Filgotinib Study Day 1 is defined as the first dose date of filgotinib which is identified by the first dispense date of filgotinib. The On-Filgotinib Study Day will be calculated from the On-Filgotinib Study Day 1 and derived as follows:

- For postdose study days of filgotinib: Assessment Date – On-Filgotinib Study Day 1 + 1
- For days prior to the first dose of filgotinib: Assessment Date – On-Filgotinib Study Day 1

3.8.2. Analysis Visit Windows

Subject visits may not occur on protocol-specified days. Therefore, for the purpose of analysis, observations will be assigned to analysis windows.

In general, the baseline value will be the last nonmissing value on or prior to the first dose date of study drug, except for the mTSS baseline value. The mTSS baseline value will be derived based on the measurements collected on or prior to the first dose date of study drug + 14 days given the potential delay in scheduling an x-ray assessment. If multiple valid, nonmissing measurements exist in the analysis window as aforementioned, in general, the last nonmissing mTSS value on or prior to the first dose date of study drug will be selected as the baseline value; If all these multiple measurements occur at post first dosing, the value closest to the first dose date will be selected as the baseline value.

For subjects who were on placebo and then re-randomized, the baseline after Week 24 will be the last nonmissing value obtained on or prior to the first dose date of filgotinib, except for the mTSS baseline value. The mTSS baseline value will be derived based on the measurements collected on or prior to the first dose date of filgotinib + 14 days given the potential delay in scheduling an x-ray assessment. If multiple valid, nonmissing measurements exist in the analysis window as aforementioned, in general, the last nonmissing mTSS value on or prior to the first dose date of filgotinib will be selected as the baseline value; If all these multiple measurements occur at post first dosing of filgotinib, the value closest to the first dose date of filgotinib will be selected as the baseline value.

For efficacy endpoints, vital signs, ECG, weight, lipids and safety laboratory data, the analysis visit windows will be applied to data collected during the ‘on-treatment’ period. The ‘on-treatment’ period is defined as the last dose date of any study drug + 7 days.

The analysis windows for on-treatment efficacy endpoints including joint count assessment, HAQ-DI (including subject’s pain assessment), subject’s global assessment (SGA), physician’s global assessment (PGA), serum CRP , exploratory patient reported outcome (PRO), and vital signs, weight, and safety laboratory data (lipid data excluded) are provided in [Table 3-1](#) and [Table 3-2](#).

Table 3-1. Analysis Visit Windows for On-Treatment Joint Count Assessment, HAQ-DI, SGA, PGA, CRP, Exploratory PRO, and Vital Signs, Weight, and Safety Laboratory Data (Lipid Data Excluded) for Subjects who were Initially Randomized to Filgotinib or Adalimumab, and Subjects who were Initially Randomized to Placebo and not Re-randomized

Analysis Visit	Nominal Study Day	Lower Limit	Upper Limit
Baseline	1	(none)	1
Week 2	15	2	22
Week 4	29	23	43
Week 8	57	44	71
Week 12	85	72	92
Week 14	99	93	106
Week 16	113	107	127
Week 20	141	128	155
Week 24	169	156	176
Week 26	183	177	197
Week 30	211	198	232
Week 36	253	233	281
Week 44	309	282	337
Week 52	365	338	≥ 365

Table 3-2. Analysis Visit Windows for On-Treatment Joint Count Assessment, HAQ-DI, SGA, PGA, CRP, Exploratory PRO, and Vital Signs, Weight, and Safety Laboratory Data (Lipid Data Excluded) for Subjects who were Initially Randomized to Placebo and Re-randomized

Analysis Visit	Nominal Study Day	Lower Limit	Upper Limit
Baseline	1	(none)	1
Week 2	15	2	22
Week 4	29	23	43
Week 8	57	44	71
Week 12	85	72	92
Week 14	99	93	106
Week 16	113	107	127
Week 20	141	128	155
Week 24	169	156	First Dose Date of Filgotinib - Study Day 1 + 1
Analysis Visit	On-Filgotinib Study Day	On-Filgotinib Lower Limit	On-Filgotinib Upper Limit
Week 26*	15	2	29
Week 30*	43	30	64
Week 36*	85	65	113
Week 44*	141	114	169
Week 52*	197	170	≥ 197

* For subjects who were on placebo and re-randomized their analysis window after Week 24 will be assigned according to On-Filgotinib Study Day, On-Filgotinib Lower Limit and On-Filgotinib Upper Limit.

The analysis windows for on-treatment mTSS and lipid data are provided in [Table 3-3](#), [Table 3-4](#), [Table 3-5](#), and [Table 3-6](#).

Table 3-3. Analysis Visit Windows for On-Treatment Lipid Data for Subjects who were Initially Randomized to Filgotinib or Adalimumab, and Subjects who were Initially Randomized to Placebo and not Re-randomized

Analysis Visit	Nominal Study Day	Lower Limit	Upper Limit
Baseline	1	(none)	1
Week 12	85	2	127
Week 24	169	128	267
Week 52	365	268	≥ 365

Table 3-4. Analysis Visit Windows for On-Treatment mTSS for Subjects who were Initially Randomized to Filgotinib or Adalimumab, and Subjects who were Initially Randomized to Placebo and not Re-randomized

Analysis Visit	Nominal Study Day	Lower Limit	Upper Limit
Baseline	1	(none)	15
Week 12	85	16	127
Week 24	169	128	267
Week 52	365	268	≥ 365

Table 3-5. Analysis Visit Windows for On-Treatment Lipid Data for Subjects who were Initially Randomized to Placebo and Re-randomized

Analysis Visit	Nominal Study Day	Lower Limit	Upper Limit
Baseline	1	(none)	1
Week 12	85	2	127
Week 24	169	128	First Dose Date of Filgotinib - Study Day 1 + 1
Analysis Visit	On-Filgotinib Study Day	On-Filgotinib Lower Limit	On-Filgotinib Upper Limit
Week 52*	197	2	≥ 197

* For subjects who were on placebo and re-randomized their analysis window after Week 24 will be assigned according to On-Filgotinib Study Day, On-Filgotinib Lower Limit and On-Filgotinib Upper Limit.

Table 3-6. Analysis Visit Windows for On-Treatment mTSS data for Subjects who were Initially Randomized to Placebo and Re-randomized

Analysis Visit	Nominal Study Day	Lower Limit	Upper Limit
Baseline	1	(none)	15
Week 12	85	16	127
Week 24	169	128	(First Dose Date of Filgotinib + 14) - Study Day 1 + 1
Analysis Visit	On-Filgotinib Study Day	On-Filgotinib Lower Limit	On-Filgotinib Upper Limit
Week 52*	197	16	≥ 197

* For subjects who were on placebo and re-randomized their analysis window after Week 24 will be assigned according to On-Filgotinib Study Day, On-Filgotinib Lower Limit and On-Filgotinib Upper Limit.

The analysis windows for On-Treatment Healthcare Resource Utilization Questionnaire (HRUQ), Treatment Satisfaction Questionnaire for Medication (TSQM) and ECG data are provided in [Table 3-7](#) and [Table 3-8](#).

Table 3-7. Analysis Visit Windows for On-Treatment HRUQ,TSQM and ECG Data for Subjects who were Initially Randomized to Filgotinib or Adalimumab, and Subjects who were Initially Randomized to Placebo and not Re-randomized

Analysis Visit	Nominal Study Day	Lower Limit	Upper Limit
Baseline	1	(none)	1
Week 12	85	2	127
Week 24	169	128	211
Week 36	253	212	309
Week 52	365	310	≥ 365

Table 3-8. Analysis Visit Windows for On-Treatment HRUQ,TSQM and ECG Data for Subjects who were Initially Randomized to Placebo and Re-randomized

Analysis Visit	Nominal Study Day	Lower Limit	Upper Limit
Baseline	1	(none)	1
Week 12	85	2	127
Week 24	169	128	First Dose Date of Filgotinib - Study Day 1 + 1
Analysis Visit	On-Filgotinib Study Day	On-Filgotinib Lower Limit	On-Filgotinib Upper Limit
Week 36*	85	2	141
Week 52*	197	142	≥ 197

* For subjects who were on placebo and re-randomized their analysis window after Week 24 will be assigned according to On-Filgotinib Study Day, On-Filgotinib Lower Limit and On-Filgotinib Upper Limit.

The analysis windows for on-treatment SF-36, FACIT-Fatigue, EQ-5D and WPAI-RA are provided in [Table 3-9](#) and [Table 3-10](#).

Table 3-9. Analysis Visit Windows for On-Treatment SF-36, FACIT-Fatigue, EQ-5D, and WPAI-RA for Subjects who were Initially Randomized to Filgotinib or Adalimumab, and Subjects who were Initially Randomized to Placebo and not Re-randomized

Analysis Visit	Nominal Study Day	Lower Limit	Upper Limit
Baseline	1	(none)	1
Week 4	29	2	57
Week 12	85	58	127
Week 24	169	128	211
Week 36	253	212	309
Week 52	365	310	≥ 365

Table 3-10. Analysis Visit Windows for On-Treatment SF-36, FACIT-Fatigue, EQ-5D, and WPAI-RA for Subjects who were Initially Randomized to Placebo and Re-randomized

Analysis Visit	Nominal Study Day	Lower Limit	Upper Limit
Baseline	1	(none)	1
Week 4	29	2	57
Week 12	85	58	127
Week 24	169	128	First Dose Date of Filgotinib - Study Day 1 + 1
Analysis Visit	On-Filgotinib Study Day	On-Filgotinib Lower Limit	On-Filgotinib Upper Limit
Week 36*	85	2	141
Week 52*	197	142	≥ 197

* For subjects who were on placebo and re-randomized their analysis window after Week 24 will be assigned according to On-Filgotinib Study Day, On-Filgotinib Lower Limit and On-Filgotinib Upper Limit.

Vital signs, weight, ECG, lipids and safety laboratory data collected in the post-treatment follow-up period will also be summarized. The analysis window for the post-treatment follow-up period is defined as from (the last dose date of any study drug + 8 days) to (the last dose date of any study drug + 30 days). If multiple valid, nonmissing measurements exist in the post-treatment follow-up visit window, then the latest record will be selected for analysis. If the chronological order cannot be determined (eg, more than 1 record on the same day with time missing), for any given subject, the value with the worst severity will be selected for categorical variable, and the average will be taken for continuous variable. Data obtained after last dose date plus 30 days will be excluded from the summaries, but will be included in the listings.

For efficacy endpoints, the same analysis visit windows will be applied to all available data collected during standard of care.

3.8.3. Selection of Non-Efficacy Data in the Event of Multiple Records in an Analysis Visit Window

Depending on the statistical analysis method, single values may be required for each analysis window. For example, change from baseline by visit usually requires a single value, whereas a time-to-event analysis would not require 1 value per analysis window.

If multiple valid, nonmissing, continuous measurements exist in an analysis window, records will be chosen based on the following rules if a single value is needed:

- In general, the baseline value will be the last nonmissing value on or prior to the first dose date of study drug, unless otherwise specified. If multiple measurements occur on the same day, the last nonmissing value prior to the time of first dose of study drug will be considered as the baseline value. If these multiple measurements occur at the same time or the time is not available, the average of these measurements (for continuous data) will be considered the baseline value.
- For postbaseline visits:
 - The record closest to the nominal day for that visit will be selected.
 - If there are 2 records that are equidistant from the nominal day, the later record will be selected.
 - If there is more than 1 record on the selected day, the average will be taken, unless otherwise specified.

If multiple valid, nonmissing, categorical measurements exist in an analysis window, records will be chosen based on the following rules if a single value is needed:

- For baseline, the last available record on or prior to the date of the first dose of study drug will be selected. If there are multiple records with the same time or no time recorded on the same day, the value with the lowest severity will be selected (eg, normal will be selected over abnormal for safety ECG findings).
- For postbaseline visits:
 - The record closest to the nominal day for that visit will be selected.
 - If there are 2 records that are equidistant from the nominal day, the later record will be selected.
 - If there is more than 1 record on the selected day, the value with the worst severity will be selected (eg, abnormal will be selected over normal for safety ECG findings), unless otherwise specified.

The rules for selecting efficacy data in the event of multiple records in an analysis visit window are specified in Section [6.1](#).

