Blood samples for biomarker analysis should be collected at Day 1, Weeks 4, 8, 12, 24, 36, and Week 52 or ET and urine samples should be collected at Day 1, Weeks 12, 24, and Week 52 or ET.

Radiographs of the bilateral hands, wrists, and feet should be taken at Screening, Weeks 12, 24, and Week 52 or ET. However, if a subject prematurely discontinues study participation and has had X-rays performed within the previous 12 weeks, then X-rays do not need to be repeated at the ET visit. Radiographs after enrollment may be done +/- 7 days of the scheduled visit. Post treatment follow-up assessments include AEs, concomitant medications, physical examination, 12-lead ECG, weight, vital signs, blood and urine sampling for safety laboratory tests, and urine pregnancy tests (females of child bearing potential only).

CCI

CCI

Test Product, Dose, and Mode of Administration:

200 mg filgotinib orally q.d.
100 mg filgotinib orally q.d.

Reference Therapy, Dose, and Mode of Administration:

Adalimumab injection (40 mg s.c.) or PTM s.c. q2w
PTM filgotinib 200 mg orally q.d.
PTM filgotinib 100 mg orally q.d.

Required Background Medication:

Stable prescription of weekly MTX as described in the inclusion criteria and administered according to the local product label/standard of care.

Criteria for Evaluation:

Safety:

Safety will be assessed by documentation of AEs, clinical laboratory tests, physical examinations, vital signs, and 12-lead ECGs during the study.

Efficacy: The primary endpoint is the proportion of subjects who achieve an ACR20 response at Week 12.

The key secondary endpoints are:

- The proportion of subjects who achieve DAS28 (CRP) \leq 3.2 at Week 12
- Change from Baseline in the HAQ-DI score at Week 12
- The proportion of subjects who achieve DAS28 (CRP) $<$ 2.6 at Week 24
- Change from Baseline in mTSS at Week 24

Pharmacokinetics: Plasma concentrations of filgotinib and its metabolite (GS-829845) will be analyzed.

Statistical Methods: The primary analysis set for efficacy analyses will be the Full Analysis Set (FAS), which includes all randomized subjects who received at least one dose of study drug.

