6.7.1.11. Hands, Wrists, and Feet Radiographs

Hands, wrists, and feet radiographs will be taken at the time points indicated in the study procedures table (Appendix 2). Note that if a subject discontinues the study early and has had X-rays performed in the <12 week period prior to discontinuation, these do not need to be repeated at ET. Radiographs performed after enrollment may be done +/-7 days of the scheduled visit.

All subjects who discontinue from investigational therapy but continue study visits and procedures, should continue to have radiographs performed as outlined in the study procedure table ([Appendix 2](#)).

The radiographs will be evaluated through central review by independent blinded assessors using the mTSS.

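### For placebo subjects switched to filgotinib, the post-Week-24 mTSS baseline rule, read literally, returns the Week 12 film when the Week 24 film is taken 1 to 14 days after the switch

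*SAP*

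**What the plan says.** SAP 3.8.2 sets a separate baseline after Week 24 for placebo subjects who are re-randomized. For mTSS it is built in three steps.

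- Candidates: "measurements collected on or prior to the first dose date of filgotinib + 14 days given the potential delay in scheduling an x-ray assessment". No earliest date is given.
- Selection: "If multiple valid, nonmissing measurements exist in the analysis window as aforementioned", then "in general, the last nonmissing mTSS value on or prior to the first dose date of filgotinib will be selected as the baseline value".
- Exception: "If all these multiple measurements occur at post first dosing of filgotinib, the value closest to the first dose date of filgotinib will be selected".

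Table 3-6, for the same subjects, opens the Week 24 mTSS window at Day 128 and closes it at 14 days after the first filgotinib dose (upper limit "First Dose Date of Filgotinib + 14) - Study Day 1 + 1"). The Week 52 window opens at On-Filgotinib Day 16.

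The Protocol Synopsis sets the film schedule: "Radiographs of the bilateral hands, wrists, and feet should be taken at Screening, Weeks 12, 24, and Week 52 or ET". Protocol 6.7.1.11 adds: "Radiographs performed after enrollment may be done +/-7 days of the scheduled visit". The switch takes place at Week 24 (Protocol 3.2), and SAP 3.8.1 dates the first filgotinib dose by its first dispensing.

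SAP 6.4.2 plans Week 52 comparisons of each continuous filgotinib group with the matching placebo-switch group, on mTSS change and on the proportion without radiographic progression. It does not say which baseline the switch groups use.

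**The concern.** The 14-day allowance is explained by delay in scheduling X-rays, so its evident purpose is to let a late Week 24 film serve as the new baseline. The selection step prevents that for most switchers. A subject who reaches Week 24 normally already has a screening film and a Week 12 film. Both precede the switch and both qualify as candidates, so the all-post-dose exception cannot apply and the late film is passed over.

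The same form of words works for the Day 1 baseline, because the film it falls back on there is the screening film, which is the right one. At Week 24 it falls back on a film about three months old.

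For an affected subject, change in mTSS, erosion score or JSN score from the new baseline would mix placebo time with filgotinib time. The same Week 12 to Week 24 progression would also count in the placebo group's Week 24 result. Where no progression is defined by a cut-off of 0.5 or 0 (SAP 6.4.2), a small added change could reclassify a subject.

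**Working it through.** **The plan's own mTSS figure.** SAP 1.3 assumes a difference of 0.4, SD 1.85, 90% power and two-sided 0.05. n per group = 2 × 1.85² × (1.960 + 1.282)² / 0.4² ≈ 449.5, so 450. This reproduces, and the present point does not touch it.

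**Applying the rule literally.** Inputs: Week 12 = Day 85, Week 24 = Day 169, Week 52 = Day 365 (SAP 4.2.1); first filgotinib dose on Day 169; screening film on Day -14 (assumed).

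| Week 24 film | Baseline, SAP 3.8.2 as written | Baseline, candidates limited to Table 3-6 Week 24 window |
|---|---|---|
| Days 162 to 169 (7 days before, up to the switch) | that film | that film |
| Days 170 to 183 (1 to 14 days after) | Day 85 film, on all 14 days | that film |
| Day 184 (15 days after) | Day 85 film | Day 85 film (none in window) |

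Late films on days 1 to 7 comply with the protocol's film window when the first dose is on the visit day. First dose + 14 days is On-Filgotinib Day 15, so in Table 3-6 a film 1 to 14 days late is a Week 24 film and not a Week 52 film. Under the literal rule it is then neither the baseline nor the outcome of the post-switch change.

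**Placebo time after the selected baseline.**
- Nominal: 169 - 85 = 84 days = 12 weeks.
- Week 12 film within ±7 days and switch within ±3 days (Protocol Appendix 2): (166 - 92)/7 = 10.6 to (172 - 78)/7 = 13.4 weeks.
- Week 12 film anywhere in its SAP window, Days 16 to 127, with a Day 169 switch: (169 - 127)/7 = 6.0 to (169 - 16)/7 = 21.9 weeks.
- Week 12 film missing: the rule falls back to the screening film, so about 24 placebo weeks are carried (168/7 = 24 from Day 1).
- Extra film at, say, Day 140: that film is chosen, leaving (169 - 140)/7 = 4.1 weeks.

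**Span to Week 52.** (365 - 85)/7 = 40 weeks instead of (365 - 169)/7 = 28. The placebo share is 84/280 = 30%.

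**Illustrative size.** The documents give neither a placebo progression rate nor a share of late films; both are assumed here. Reading the planning difference of 0.4 over 24 weeks as linear placebo progression, with none on filgotinib, adds 0.4 × 12/24 = 0.2 units per affected subject. If 10% to 50% of switchers have late films, the group mean shifts by 0.02 to 0.10. Letting the rate run from 0.2 to 0.8 per 24 weeks gives 0.1 to 0.4 units per affected subject and 0.01 to 0.20 on the mean.

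For scale, with at most 450/2 = 225 subjects in a switch group against 450, and borrowing the Week 24 SD, the SE of a difference is 1.85 × √(1/225 + 1/450) ≈ 0.15.

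**The case against.** **A reading that avoids the problem.** SAP 3.8.2 assigns observations to visit windows, and the selection rule speaks of several measurements in a window. If that window is the Table 3-6 Week 24 window, whose upper limit matches the baseline allowance exactly, the Day 85 film is not a candidate and a single late film is the baseline. Appendix 3 provides for repeat X-rays at a visit, which would give several measurements a natural meaning. This fits the likely intent but not the wording: the window meant is the one just described, and that has only an upper limit. The hedge that the rule applies in general names no alternative, so it leaves the choice to the programmer.

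**No named result is shown to be affected.** This stands. A reader might infer that 12 weeks of placebo damage is in fact credited to filgotinib at Week 52. The documents do not support that, because SAP 6.4.2 does not say that the Week 52 comparisons use the new baseline. The MMRM in SAP 6.3.2, which takes successive post-baseline visits, and the mTSS derivation in Appendix 3, which mentions no second baseline, both sit more easily with the Day 1 baseline. Against that, SAP 3.8.2 expressly defines an mTSS baseline after Week 24. The question is open.

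**Other stronger readings fail too.** The 14-day allowance is not wholly without effect: in Table 3-6 it assigns the late film to Week 24 and keeps it out of Week 52. A late film does not always bring in 12 placebo weeks; that needs a readable Week 12 film and none between it and the switch. Nor can late films be called routine: the protocol permits them, but films before or on the switch date are equally permitted and are unaffected.

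**The size is probably modest.** This also stands. At the planning rate, even a 50% late share moves the mean by 0.10, about two-thirds of the illustrative SE.

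**Conclusion.** The rule is wrong as written. For a film date the protocol allows, it passes over the film that Table 3-6 calls Week 24 and takes one about 12 weeks older, which defeats the stated reason for the allowance. The reach is narrow: post-switch mTSS, erosion and JSN changes measured from the new baseline, in switched subjects with late films. The primary endpoint, the Week 24 mTSS tests in the hierarchy and the sample size are unaffected.

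The 12-week and 40-versus-28-week figures follow from nominal visit days. The shifts in the mean rest on assumed progression rates and late-film shares and should be read only as orders of magnitude. Whether the Week 52 switch-group comparisons are biased depends on a choice of baseline that the SAP leaves unstated. That omission needs closing in its own right.

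**What to change.** In SAP 3.8.2, for re-randomized placebo subjects:

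- Limit candidates for the post-Week-24 mTSS baseline to the Table 3-6 Week 24 window, Day 128 to 14 days after the first filgotinib dose.
- Within it, take the last film on or before the first filgotinib dose; if there is none, the earliest film after it. This keeps the SAP's preference for a pre-dose baseline. A closest-film rule would not: it would choose a film 1 day after dosing over one 3 days before.
- Use an earlier film only if none falls in the window.

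In SAP 6.4.2, state which baseline the Week 52 mTSS and no-progression comparisons use for the switch groups.

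For films 1 to 14 days late, the placebo time carried past the baseline falls from a nominal 84 days to 0. The price is that up to 14 days on filgotinib may precede the baseline film. The change costs a few sentences and some programming, with no new data. If the SAP is already final, SAP section 1 provides for recording the change in the CSR.
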